#### 4.5 Statistical Analysis

A 4 (group: CR-CAF vs. CR vs. CAF vs. PLA) x 2 (time: pre- vs. post- training) repeated measures analysis of variance (ANOVA) will be used to determine differences between groups over time for the dependent variables of muscle thickness, muscle strength, muscle endurance and diet. If significant interactions are detected, a one-factor ANOVA on absolute change scores ( $\Delta = \text{post mean} - \text{pre mean}$ ) will be performed to confirm the interaction. A one-factor ANOVA will be used to assess baseline data and training volume. Significance is set *a priori* at an alpha level of  $p < 0.05$ . Cohen's *d* effect size (ES) for significant main effects and interactions will be calculated as  $\text{post-training mean} - \text{pre-training mean} / \text{pooled pre-training standard deviation mean}$  (Cohen, 1992). An ES of 0.00-0.19 is considered trivial, 0.20-0.49 is considered small, 0.50-0.79 is considered moderate, and  $\geq 0.80$  is considered large (Cohen, 1992). Statistical analyses will be performed using IBM® SPSS® Statistics, v. 24.

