## 4. Methods

### 4.1 Participants

An *a priori* power analysis (G\*Power v. 3.1.5.1) indicated that 48 participants are required. This calculation is based on a small effect size (Cohen's  $f = 0.25$ ), an alpha level of .05, and a  $\beta$ -value of 0.8 for a repeated measures, within-between analysis of variance (ANOVA) design. Males (18-30 years of age) who have been performing structured resistance training ( $> 3x/week$  for  $\geq 6$  months) prior to the start of the study will be recruited. Resistance trained participants are being recruited to help reduce the influence that neuromuscular learning has on changes in muscle mass and muscle performance over time. Prior to the start of supplementation and training, participants will fill out a questionnaire which assesses their readiness for participation in resistance training. Participants will also fill out a leisure time exercise questionnaire, which indicates the average number of times that strenuous (i.e. heart beats rapidly), moderate (i.e. not exhausting), and mild exercise (i.e. minimal effort) is performed per week. Participants will be excluded from the study if they have taken medications that affect muscle biology or creatine monohydrate  $\leq 12$  weeks prior to the start of resistance training and supplementation; if they have diseases that are known to affect muscle biology (i.e. Crohn's Disease), if they have pre-existing kidney or liver abnormalities, or if they plan to travel  $\geq 1$  week during the study where they have no access to a fitness facility. Habitual caffeine consumers are being included because regular caffeine consumption does not negate the beneficial effects of caffeine supplementation. Furthermore, habitual caffeine consumers who withdraw from caffeine may experience adverse symptoms which could negatively affect exercise performance. Participants will be instructed not to change their habitual diet or engage in additional physical activity that is not part of their normal daily routine or consume non-steroidal anti-inflammatory drugs during resistance training and

supplementation, as these interventions can affect muscle protein synthesis. The study will be approved by the Research Ethics Board at the University of Regina. Participants will be informed of the risks and purposes of the study before written consent is obtained.

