#### **4.2 Research Design**[L][SEP]

The study will be a double-blind, repeated measures design. In order to minimize group differences, participants will be matched according to age and weight and be randomized on a 1:1:1:1 basis to one of four groups: Creatine + Caffeine (CR-CAF; 0.1 g/kg of creatine monohydrate powder + 3 mg/kg of caffeine [micronized powder]); Creatine (CR; 0.1 g/kg of creatine monohydrate powder + 3 mg/kg of caffeine placebo [micronized cellulose powder]), Caffeine (CAF; 3 mg/kg of caffeine + 0.1 g/kg of creatine monohydrate placebo [maltodextrin]) or placebo (PLA; 0.1g/kg creatine monohydrate placebo + 3 mg/kg of caffeine placebo). An individual, blinded to supplement and group allocation, will be responsible for the preparation of study kits. Each study kit will contain the participants supplement for the duration of the study, detailed supplementation instructions, measuring spoons, supplementation compliance log, daily caffeine consumption log and a resistance training log. Supplement powders will be similar in energy content, color, taste, texture, and appearance. The creatine dosage of 0.1 g/kg has previously been shown to be effective for increasing muscle mass and muscle performance. The caffeine dosage of 3 mg/kg has been shown to increase muscle performance. Participants will be instructed to refrain from additional caffeine sources  $\geq 3$  hour prior to consuming their supplement so that a valid estimate regarding the effects of caffeine supplementation on muscle can be made. On training days, participants will mix their supplement powder in water and consume the solution 60 minutes prior to exercise. Sixty minutes was chosen because this is the approximate time it takes for peak plasma caffeine concentrations to occur after caffeine ingestion and pre-exercise

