creatine supplementation has a beneficial effect on muscle performance. On non-training days, participants will refrain from consuming their supplement as the purpose of the study is to investigate the effects of pre-exercise creatine and caffeine co-supplementation. Adherence with the supplementation protocol will be assessed using compliance logs. Habitual daily caffeine consumption will be recorded using caffeine logs. Upon completion of the study, participants will be asked whether they thought they were administered creatine and caffeine, creatine, placebo, or unsure about what supplement they consumed. The primary dependent variables that will be measured at baseline and after the intervention include: (1) muscle thickness (elbow and knee flexors and extensors; ultrasonography), (2) muscle strength (1-RM leg press, chest press) and (3) muscle endurance (leg press and chest press; maximum number of repetitions performed for 1 set using 50% baseline 1-RM). In addition, participants will fill out a 3-day food diary during the first and final week of supplementation and training to determine whether total energy (kcal) and macronutrient intake changed over time.

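### Section 4.5 plans no comparison that isolates the effect of co-supplementation, although the four arms cross creatine with caffeine

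*Protocol*

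**What the plan says.** Protocol section 4.2 has participants "randomized on a 1:1:1:1 basis to one of four groups": both supplements (CR-CAF), creatine with caffeine placebo (CR), caffeine with creatine placebo (CAF), and both placebos (PLA). Each supplement has its own placebo, so the arms form a complete 2 x 2. The same section explains why nothing is taken on non-training days: "as the purpose of the study is to investigate the effects of pre-exercise creatine and caffeine co-supplementation".

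Section 4.5 sets the main analysis as "A 4 (group: CR-CAF vs. CR vs. CAF vs. PLA) x 2 (time: pre- vs. post- training) repeated measures analysis of variance". If an interaction is significant, a one-factor ANOVA on post-minus-pre change is run to confirm it. The effect size is the post mean minus the pre mean over a pooled pre-training SD. The section names no creatine term, caffeine term, creatine-by-caffeine term, planned contrast or pairwise comparison.

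Section 4.1 reports a power analysis that "indicated that 48 participants are required", with f = 0.25, "an alpha level of .05" and a "value of 0.8 for a repeated measures, within-between analysis of variance (ANOVA) design".

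**The concern.** A trial of co-supplementation has to say what the combination does. Two questions fit that word. One is whether the joint effect is more or less than the sum of the separate effects (the creatine-by-caffeine interaction). The other is whether the combination beats each supplement alone (CR-CAF vs CR, CR-CAF vs CAF). Section 4.5 plans neither.

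Suppose creatine works and caffeine does nothing. CR-CAF and CR both improve, the omnibus test is likely to be significant, and the result can be reported as a benefit of co-supplementation although caffeine added nothing. If instead caffeine cancels creatine, the same test is just as likely to be significant, and the written sequence gives no step that tells the two situations apart. Any comparison that does so would be chosen after the data are seen.

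**Working it through.** **Inputs.** From section 4.1: N = 48, f = 0.25, alpha 0.05, and 0.8, which is labelled a beta-value and read here as power. From section 4.2: four arms, 1:1:1:1, so 12 per arm. From section 4.5: two time points. Assumed because not stated: pre-post correlation rho = 0.5 and no sphericity correction (none is needed with two time points).

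**1. Reproduce N = 48.** For the within-between interaction with k = 4 groups and m = 2 times:

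- lambda = f² x N x m / (1 − rho) = 0.0625 x 48 x 2 / 0.5 = 12
- df1 = (k − 1)(m − 1) = 3; df2 = (N − k)(m − 1) = 44
- power = 0.803 at N = 48 and 0.760 at N = 44

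So 48 is the N for the 3-df group-by-time test at rho = 0.5. The figure depends on rho: the required N would be 92, 68, 32 or 24 at rho = 0, 0.3, 0.7 or 0.8.

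**2. What the omnibus test can tell apart.** At rho = 0.5 the change-score SD equals the raw SD. Lambda = 12 then means that the arm mean changes have an SD of 0.5, since 48 x 0.5² = 12. Scale four patterns to that size, with mean changes in change-score SD units and power at alpha 0.05 for each test taken alone:

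| Pattern | CR-CAF, CR, CAF, PLA | Omnibus, 3 df | Creatine x caffeine, 1 df | CR-CAF vs CR, 1 df |
|---|---|---|---|---|
| Creatine only | 1, 1, 0, 0 | 0.80 | 0.05 | 0.05 |
| Additive | 1.414, 0.707, 0.707, 0 | 0.80 | 0.05 | 0.40 |
| Combination only | 1.155, 0, 0, 0 | 0.80 | 0.50 | 0.79 |
| Caffeine cancels creatine | 0, 1.155, 0, 0 | 0.80 | 0.50 | 0.79 (negative direction) |

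Values of 0.05 are the alpha level: that contrast is truly zero. The omnibus column is constant although the four patterns give different answers about the combination. The two contrasts do separate them.

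**3. Where the contrast figures come from.**

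- SE of the interaction contrast = sqrt(4/12) = 0.577; SE of a pairwise contrast = sqrt(2/12) = 0.408.
- Combination only: 1.155/0.577 = 2.0, so lambda = 4 and power is 0.50. Pairwise: 1.155/0.408 = 2.83, so lambda = 8 and power is 0.79.
- For 80% power on the interaction in a one-arm pattern, the same calculation gives N = 100.

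**4. Does the follow-up help?** With two time points, the group-by-time F and the one-factor F on change scores are algebraically the same. In a simulated data set of 48, both gave F(3,44) = 3.472. The follow-up therefore confirms nothing and does not locate the difference.

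**5. Does the effect size help?** It standardises post minus pre and is not a difference between arms.

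**The case against.** **The estimand is partly inferred.** The visible statement of purpose is a clause explaining the dosing days, and it does not mention synergy. This stands: the documents do not show that the interaction is the one intended estimand. The gap remains all the same, because the combination-versus-single comparisons are not planned either.

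**The four-level factor is not an error.** This stands. The 4-level and 2 x 2 codings are the same saturated model, with the same cell means and 44 error df, and the factorial contrasts can be formed from either. The defect is the absence of any named contrast.

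**The omnibus test contains the interaction.** A reader might infer that nothing planned would respond if caffeine blunted creatine. That is too strong: the omnibus has power 0.80 for that pattern, against 0.50 for the interaction contrast. What is missing is attribution, not sensitivity.

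**Factorial coding would raise power.** This is a tempting inference. At noncentrality 12 a 1-df main-effect test has 92% power against 80% for the omnibus, but only if all signal lies in one supplement, which is the case where the combination adds nothing. In a one-arm pattern the noncentrality splits equally over three factorial terms. Each then has about 50% power, and the chance that any is significant at 0.05/3 is 67%, against 80% for the omnibus. Three unadjusted factorial tests would also carry a familywise error of about 14% (1 − 0.95³ = 0.143). Replacing the ANOVA is a trade-off, not a correction.

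**A separate SAP may name contrasts.** It may. But section 4.5 itself fixes the model, the follow-up, alpha and the effect size, and the follow-up it fixes is redundant.

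**Conclusion.** The point holds in this form: no analysis in section 4.5 isolates the effect of the combination. The omnibus test has power 0.80 under four patterns with different meanings, its follow-up repeats it, and the effect size does not compare arms. The redundancy of the follow-up and the missing contrasts rest on the text alone. The power figures rest on f = 0.25, rho = 0.5, 12 completers per arm and 0.8 read as power.

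The documents do not support the stronger conclusions that the 4 x 2 ANOVA is the wrong model, that it is blind to interference, or that N = 48 is miscalculated. N = 48 reproduces for the test it was set for. It gives only about 50% power for the interaction if one arm differs from the other three. The matter should be put right before analysis. The data to do so will be collected in any case.

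**What to change.** Keep the 4 x 2 ANOVA. In section 4.5, replace the one-factor ANOVA on change scores with contrasts on change, fixed in advance:

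- creatine x caffeine (x time), i.e. (CR-CAF − CR) − (CAF − PLA), for synergy or interference;
- CR-CAF vs CR and CR-CAF vs CAF, for the combination against each supplement alone.

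Report each with an estimate and 95% CI. State the multiplicity control across the contrasts (for example Holm) and whether they wait on a significant omnibus result. Say that synergy or interference will be claimed only from the interaction contrast, and that its non-significance will not be read as no interaction. Add a sentence to section 4.1 that N = 48 was set for the omnibus test.

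The cost is wording in two sections, with the same participants, data and software. The downside is a few more tests at an adjusted alpha, and an open admission that the interaction is imprecise (SE 0.577 change-score SD). No gain in power should be offered as a reason for the change.

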Precise markings using a permanent marker will be made on a transparency film sheet to ensure that the exact identical site is measured before and after the resistance training program by the same researcher. Water-soluble transmission gel (EcoGel 200, Eco-Med Pharmaceutical Inc., Mississauga, Ontario, Canada) will be placed on the measurement site to provide acoustic contact with the surface of the muscle. An 8-MHz scanning transducer head will be placed perpendicular to the muscle area. When the image is produced on the screen, the image on the monitor will be frozen. With the image frozen, a cursor will be enabled to quantify muscle thickness (cm) at three sites: proximal, mid and distal, as determined by divisions (1cm) on the monitor. Muscle thickness measurements will be determined from the monitor screen by measuring the distance from the bottom of the subcutaneous adipose layer to the surface of the humerus for the elbow flexors and extensors and to the surface of the femur for the knee flexors and extensors. Three muscle thickness measurements will be taken at each of the four muscle group sites. The values at each of three sites will be averaged to quantify one muscle thickness value that will be used for analysis.

The same researcher will perform all measurements. The reproducibility (coefficient of variation; intraclass correlation coefficient) of muscle thickness measurements will be determined

prior to supplementation and training by assessing 10 participants, > 24 hours apart. Baseline and post-testing muscle thickness measurements will be performed prior to assessing 1-RM strength and endurance. Post-testing muscle thickness measurements will be performed  $\geq$  48 hours after the last resistance training session.

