#### **4.42 Muscular Strength and Endurance**

Machine-based leg press and machine-based chest press 1-RM will be performed in the Exercise Physiology Laboratory, University of Regina. To determine the 1-RM, participants will perform a 5-minute warm-up on a stationary cycle ergometer at a self-selected intensity and light passive stretching. Participants will then perform two warm-up sets of each exercise in the following order: 1 set of 10 repetitions using a load, which will be determined by each participant to be comfortable, and 1 set of 5 repetitions using a heavier weight. Two-minutes after the warm-up sets, the load will be progressively increased for each subsequent 1-RM attempt. Participants will rest (passively) for 2 minutes between 1-RM attempts. Participants will reach their 1-RM in  $\leq$  6 sets. To determine muscle endurance, participants will perform repetitions to volitional fatigue (1 set) using 50% baseline 1-RM for the squat and chest press.

To measure leg press 1-RM and endurance, participants will be positioned in a vertical leg press machine with both feet pushing up against the machine. Following a demonstration, participants will be instructed to lower the weight until an internal angle at the knees of  $90^\circ$  is achieved before returning to the upright position. The reproducibility (coefficient of variation; intraclass correlation coefficient) of leg press 1-RM will be determined prior to supplementation and training by assessing 10 participants, > 24 hours apart.

For chest press 1-RM and endurance, participants will be positioned in the bilateral chest press machine with both feet placed on the floor. Following a demonstration, participants will be

instructed not to lift their hips off the bench or arch their back during the lift. Participants will be instructed to grasp the bars (overhand grip) approximately shoulder width apart and push the load away from the body until full extension without locking the elbows and then lower the load back to the starting position. The reproducibility (coefficient of variation; intraclass correlation coefficient) of chest press 1-RM will be determined prior to supplementation and training by assessing 10 participants, > 24 hours apart.

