#### **4.43 Diet**

Dietary intake will be recorded during the first and final week of supplementation and resistance training to assess differences in total energy and macronutrient composition between groups. Participants will use a 3-day food booklet to record food intake for two weekdays and one weekend day. Participants will be instructed to record all food items, including portion sizes consumed for the three designated days. My FitnessPal will be used to analyze 3-day food records.

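### For muscle thickness, strength and endurance, the planned ANOVA only subtracts the baseline; adjusting for it by ANCOVA is a nearly free gain in precision unless the pre-post correlation times the post/pre SD ratio is near 1

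*Protocol*

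**What the plan says.** Protocol section 4.5 names one model for muscle thickness, strength, endurance and diet: a four-group by two-time "repeated measures analysis of variance (ANOVA) will be used to determine differences between groups over time". If the interaction is significant, it is to be confirmed by "a one-factor ANOVA on absolute change scores". Baseline data are compared between groups by one-factor ANOVA and are not otherwise used. No baseline covariate appears anywhere in the protocol.

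Section 4.1 bases the 48 participants on "a repeated measures, within-between analysis of variance (ANOVA) design", so the analysis and the sample size agree with each other. Section 4.2 introduces thickness, strength and endurance with "The primary dependent variables that will be measured at baseline and after the intervention include", so a pre-treatment value of each is already planned.

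**The concern.** With two time points, the group-by-time F statistic equals the F statistic of the one-way ANOVA on post minus pre. The confirmatory step in section 4.5 is therefore the same test again. Both set the regression slope of post on baseline to 1 in every group. If the true slope differs from 1, chance baseline differences between groups of 12 are over- or under-corrected. This averages out over randomisation but adds noise. An ANCOVA estimates the slope from the data and removes that noise at the price of one error degree of freedom.

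Precision is what is at stake, not validity. It matters because the trial is small and its planned power has almost no margin.

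**Working it through.** **Inputs.** From section 4.1: N = 48, Cohen's f = 0.25, alpha 0.05, and 0.8, which is printed as a beta-value and read here as power. From section 4.2: four groups, 1:1:1:1 (12 each), two measurements. Not stated, so varied here: the pre-post correlation rho and the ratio k = post SD / pre SD.

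**1. Reproduce N = 48.** For the within-between interaction with m = 2 times, the noncentrality is lambda = f² × N × m / (1 − rho), with 3 and N − 4 df. At rho = 0.5 and N = 48, lambda = 0.0625 × 48 × 2 / 0.5 = 12 and power is 0.803. It is 0.793 at N = 47 and 0.760 at N = 44. In multiples of 4, other correlations would need N = 92 (rho 0), 68 (0.3), 32 (0.7), 24 (0.8) or 16 (0.9). So rho = 0.5 is the value that fits. It is an inference about the calculation and says nothing about how these outcomes behave.

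**2. Compare the error variances.** With pre SD = 1 and post SD = k:
- change score: 1 + k² − 2·rho·k
- ANCOVA residual: k²(1 − rho²)
- difference: (1 − rho·k)²

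The ANCOVA variance is therefore never larger asymptotically, and the two are equal only when rho·k = 1. With k = 1 the ratio reduces to (1 + rho)/2.

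| Variance ratio, ANCOVA / change | rho 0.5 | 0.7 | 0.8 | 0.9 |
|---|---|---|---|---|
| k = 0.9 | 0.668 | 0.751 | 0.788 | 0.810 |
| k = 1.0 | 0.750 | 0.850 | 0.900 | 0.950 |
| k = 1.1 | 0.818 | 0.921 | 0.968 | 1.000 |
| k = 1.2 | 0.871 | 0.966 | 0.997 | 0.977 |
| k = 1.4 | 0.942 | 1.000 | 0.980 | 0.846 |

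For k = 1, confidence intervals are multiplied by the square root of the ratio: 0.87, 0.92, 0.95 and 0.97.

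**3. Power with the protocol's f = 0.25 kept.** With k = 1, lambda = 6 / (1 − rho). Simulated power, change score vs ANCOVA:
- rho 0.3: 0.641 vs 0.830
- rho 0.5: 0.803 vs 0.903
- rho 0.7: 0.963 vs 0.982
- rho 0.8: 0.997 vs 0.999

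**4. Power with the change-score test held at about 0.80.** This asks what ANCOVA adds if the trial really has its nominal power, whatever rho is. Lambda for the change score is 12, with 40,000 trials per cell and ANCOVA on 3 and 43 df. Change-score power came out at 0.800 to 0.806 in every cell.

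| ANCOVA power | rho 0.5 | 0.7 | 0.8 | 0.9 |
|---|---|---|---|---|
| k = 0.9 | 0.935 | 0.903 | 0.885 | 0.878 |
| k = 1.0 | 0.904 | 0.860 | 0.837 | 0.811 |
| k = 1.1 | 0.876 | 0.827 | 0.805 | 0.792 |
| k = 1.2 | 0.850 | 0.807 | 0.796 | 0.803 |
| k = 1.4 | 0.816 | 0.790 | 0.802 | 0.862 |

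For k of 1.1 to 1.2 and rho of 0.7 to 0.9, the difference from the change score runs from +2.6 points (0.827 vs 0.801) to −1.1 points (0.792 vs 0.803). The small losses come from the lost df and from chance baseline imbalance, which inflates the variance by about 1/(48 − 4 − 2) = 1/42, or 2.4%.

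**5. Type I error.** Under the null (k = 1.0 and 1.2, rho 0.3 to 0.9), rejection was 0.047 to 0.051 for the change score and 0.049 to 0.051 for ANCOVA.

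**6. In participants.** At rho = 0.5 with equal SDs, ANCOVA would reach 80% power with 40 participants rather than 48.

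**The case against.** The strongest reply is that nothing here is wrong. The planned test is standard, unbiased over randomisation and consistent with its own sample-size calculation, and the protocol gives no figure from which the loss can be sized. The 10-point gain needs rho = 0.5 and equal SDs, neither of which is stated. For thickness, the protocol's own procedure points to a high correlation, since the "exact identical site is measured before and after the resistance training program by the same researcher". If f = 0.25 holds at such a correlation, power is already above 0.96 and there is almost nothing to gain. All of this stands, and it is why the point is one to consider and not an error.

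The pattern is also not simply that a lower correlation brings a larger gain. At k = 1.4 the gain is 1.6 points at rho = 0.5 (0.816 vs 0.800) but 6.0 at rho = 0.9 (0.862 vs 0.802). Endurance could have k above 1, because "participants will perform repetitions to volitional fatigue (1 set) using 50% baseline 1-RM" fixes the load while strength may rise. That too stands: what governs the variance difference is the distance of rho·k from 1.

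Three practical objections are minor. The N in section 4.1 would describe the sensitivity model rather than the primary one. ANCOVA gives no time main effect, which the section 4.5 effect-size definition uses. Six pairwise differences among four groups raise multiplicity. The first two are met by keeping the repeated-measures ANOVA, and the third by naming the contrasts. ANCOVA does assume a common linear slope, but the planned test also assumes a common slope and fixes it at 1.

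None of this gives a reason to prefer the fixed slope. The outcomes may differ in rho and k, and ANCOVA removes the need to guess either.

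**Conclusion.** The point holds, as a suggestion to consider and not as an error. Section 4.5 itself fixes the model, so an unseen analysis plan does not leave the choice open.

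The gain is about 10 power points at the correlation that reproduces N = 48, assuming equal SDs. With equal SDs and change-score power at 0.80, it is 1 to 6 points for rho of 0.7 to 0.9. It is close to nil near rho·k = 1, or when the planned effect size already gives power near 1. The worst simulated loss is about 1 point. Which case applies to which outcome cannot be known from the protocol, because neither rho nor the SDs are given. Confidence in the size is therefore medium; the algebra itself is exact.

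**What to change.** In section 4.5, for muscle thickness, strength and endurance, make the primary model an ANCOVA of the post-training value on the four-level group, with that outcome's own baseline as covariate (1 df). Report adjusted group differences with 95% confidence intervals, name which contrasts are of interest, and keep the repeated-measures ANOVA as a sensitivity analysis. Add a sentence to section 4.1 saying that the 48 was calculated for the repeated-measures test.

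Do not apply this to diet. Section 4.43 says "Dietary intake will be recorded during the first and final week of supplementation and resistance training", so the first record is not a pre-treatment baseline.

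Optionally, since "participants will be matched according to age and weight" (section 4.2), age and weight may be added for 2 further df. Their prognostic value is not stated, so no loss from omitting them is claimed. If they predict nothing, power falls by about 1 point (simulated 0.907 to 0.897 at rho 0.5; 0.845 to 0.831 at rho 0.8). At an assumed partial R² of 10% it rises (0.906 to 0.923; 0.838 to 0.870).

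The cost is wording and one error df (44 to 43). No new measurement, visit or participant is needed.

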#### **4.3 Resistance Training Program**

Participants will follow the same periodized, resistance training program for 6 weeks. The program will consist of three sets of 6, 8, 10 repetitions to muscle fatigue in order. Resistance training will start on the first day of supplementation and will consist of a split routine involving whole body musculature. Day 1 will involve chest and biceps musculature and include the following exercises in order: machine-based chest press, free weight incline bench press or dumbbell press, free-weight flat dumbbell press, machine-based pec-dec, free-weight standing barbell curl, free-weight alternate arm dumbbell curl and machine-based preacher curl. Day 2 will involve leg and core musculature and include the following exercises in order: free-weight squat, machine-based leg press, machine-based leg extension, machine-based leg curl, machine-based calf raise, and

machine-based weighted abdominal crunches. Day 3 will serve as a rest day from training. Day 4 will involve back and triceps musculature and include the following exercises in order: body weight or weight-assisted chin-ups, machine-based seated row, machine-based lat pull-down, free-weight alternate dumb-bell row, free-weight close-grip bench press, machine-based cable triceps bar extension, and machine-based cable triceps rope extension. Day 5 will involve shoulder and core musculature and include the following exercises in order: free-weight dumbbell press, free-weight upright row, free-weight shrugs, free-weight or machine based lateral deltoid flys, free-weight or machine-based rear deltoid flys and machine-based weighted abdominal crunches. Day 6 will serve as a rest day from training. This cycle will be repeated for 6 weeks. Participants will maintain training logs to ensure adherence and compliance to the study and to determine total training volume (load x repetitions x sets).

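### Training volume is compared by an unadjusted one-factor ANOVA although baseline 1-RM and body weight are on hand; the test is valid but gives away precision

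*Protocol*

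**What the plan says.** Section 4.3 has participants keep training logs, in part "to determine total training volume (load x repetitions x sets"). Nothing scales that total to a man's strength or body mass.

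Section 4.5 names the test: "A one-factor ANOVA will be used to assess baseline data and training volume". No covariate is mentioned. Thickness, strength, endurance and diet are instead analysed by a 4 (group) x 2 (time) repeated measures ANOVA. The protocol thus fixes the method for volume and does not leave it open for a later analysis plan.

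On design, section 4.2 says "participants will be matched according to age and weight and be randomized on a 1:1:1:1 basis to one of four groups". Strength is not a matching factor. Leg press and chest press 1-RM are measured at baseline (sections 4.2 and 4.42), and body weight is known because it drives both matching and dosing. On size, section 4.1 states that the power analysis "indicated that 48 participants are required", which is 12 per arm. Training volume is not among the primary dependent variables listed in section 4.2.

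**The concern.** In a pre/post analysis each man serves as his own control, so stable differences between men drop out of the group-by-time test. Training volume cannot be handled that way, because nothing is logged before supplementation starts. A total measured in kilograms will reflect, to some degree, how strong and how large a man was on entry. Eligibility in section 4.1 sets age, training frequency and training history, but no strength or weight range. In a one-factor ANOVA all of that variation sits in the error term.

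Matching on weight does not solve this. Balancing a predictor across arms and then leaving it out of the model keeps its variance in the residual. Strength is neither balanced by design nor adjusted for, and with 12 per arm a chance imbalance in strength would feed straight into the volume comparison.

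What is at stake is how much the volume comparison can say about whether the arms trained alike. With wide intervals, a non-significant result leaves sizeable differences open.

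**Working it through.** **Inputs from the protocol.** N = 48, four arms, 12 per arm; alpha 0.05; f = 0.25; the stated β of 0.8 is read as power (section 4.1). **Assumed, not in the documents:** the correlation r of volume with baseline strength and weight, shown from 0.3 to 0.8, and a 0.75 SD caffeine effect as illustration.

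**Step 1. The plan's own figure.** For the group-by-time interaction, λ = f²·N·m/(1−ρ) with m = 2 time points and ρ = 0.5 (assumed; the protocol gives none):

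- N = 48: λ = 0.0625 × 48 × 2/0.5 = 12.0, df 3 and 44, power 0.803.
- N = 44: λ = 11.0, df 3 and 40, power 0.760.

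So 48 is reproduced, but for the interaction, where each man is his own control.

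**Step 2. The planned volume test at the same f.** One-factor ANOVA: λ = N·f² = 48 × 0.0625 = 3.0, df 3 and 44, power 0.254. The sample size calculation therefore does not cover this test.

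**Step 3. Precision of the planned pairwise comparison**, in SD of volume, using the pooled error with 44 df:

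- Standard error = √(2/12) = 0.408.
- 95% CI half-width = 2.015 × 0.408 = 0.82.
- Detectable difference at 80% power (noncentral t, noncentrality 2.865) = 2.865 × 0.408 = 1.17.

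**Step 4. With adjustment.** The residual SD is multiplied by √(1−r²), with 43 df for one covariate. The detectable difference is 2.866 × 0.408 × √(1−r²). For the illustrative effect, two arms lie 0.375 SD above the mean and two lie 0.375 SD below it, so f = 0.375 and λ = 48 × 0.375²/(1−r²) = 6.75/(1−r²). The last column is 1/(1−r²), the sample size multiple that the adjustment is worth.

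| r (assumed) | √(1−r²) | Detectable pairwise difference (SD) | λ | Omnibus power | Sample multiple |
|---|---|---|---|---|---|
| none (planned) | 1.00 | 1.17 | 6.75 | 0.53 | 1.00 |
| 0.3 | 0.954 | 1.12 | 7.42 | 0.57 | 1.10 |
| 0.5 | 0.866 | 1.01 | 9.00 | 0.67 | 1.33 |
| 0.6 | 0.800 | 0.94 | 10.55 | 0.74 | 1.56 |
| 0.7 | 0.714 | 0.84 | 13.24 | 0.84 | 1.96 |
| 0.8 | 0.600 | 0.70 | 18.75 | 0.95 | 2.78 |

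A second covariate (42 df) changes power by about 0.001. The table ignores the small extra variance from chance covariate imbalance.

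**The case against.** The strongest reply is that nothing here is an error. A one-factor ANOVA on randomized arms is valid and unbiased, training volume is not a primary variable, and the primary pre/post analyses are untouched. All of that stands, and it limits the point to an efficiency gain.

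Second, the size of the gain depends on a correlation that the documents do not supply. Logged volume also varies with sessions completed and with the exercise options chosen, either of which could lower r. At r = 0.3 the gain is small (power 0.53 to 0.57), and much of the weakness comes from having 12 men per arm. This stands too.

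Third, weight is partly handled by matching. That is right for balance between arms. It does not extend to the error term of the planned test, or to strength.

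A reader might infer more than the text supports:

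- **That size differences overwhelm the comparison, or that a null result says almost nothing.** This needs a high r, which is undocumented. The ±0.82 SD also belongs to 12 v 12 contrasts; for caffeine v no caffeine (24 v 24) the unadjusted interval is 2.015 × √(2/24) = ±0.58 SD. Nor does section 4.5 propose to conclude equality from a non-significant test.
- **That volume is the only performance measured under the supplement.** Sections 4.41 and 4.42 time post-tests from the last training session (at least 48 hours) and do not say whether test days are dosed. The inference is reasonable but not stated, and the post-tests still reflect six weeks of supplemented training.
- **That "body weight or weight-assisted chin-ups" are mis-scored.** The protocol does not say how load is recorded for them. This is an unstated detail for one of 26 listed exercises, not a wrong rule.

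**Conclusion.** The point holds as a precision issue on a supporting variable. The protocol fixes an unadjusted test where a better one is available from data already collected. The raw comparison detects 1.17 SD pairwise at 80% power. Adjustment would bring this to about 1.12 SD if r is 0.3, 1.01 SD if r is 0.5 and 0.70 SD if r is 0.8, so the benefit runs from slight to large. It rests on the assumed r, on 12 analysed men per arm, and on a linear relation of volume to the covariates. There is no systematic bias and no consequence for the primary analyses.

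**What to change.** In section 4.5, take training volume out of the one-factor ANOVA sentence. Analyse it by ANCOVA with group, baseline 1-RM and body weight, stating beforehand how leg press and chest press 1-RM enter the model (for example as a sum). Report adjusted group differences with 95% CIs, and add that a non-significant result will not be taken as evidence of equal training.

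The cost is a sentence or two of wording and one or two degrees of freedom. No new measurement is needed.
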